Session I of an intravenous fentanyl citrate administration, with at least a one week washout interval between Study Sessions.

The study products are:

- Single intravenous (100 µg) administration of fentanyl citrate (50 µg/mL)
- Duragesic® TDDS containing fentanyl (25 µg/h) to be worn for 3 days (72h)
- Mylan fentanyl TDDS (Generic) containing fentanyl (25 µg/h) to be worn for 3 days (72h)

Each Subject will be his/her own control.

Administration of naloxone injection will be used to test for withdrawal prior to using any study products, and to be used emergently in case of fentanyl toxicity. Naltrexone oral tablets will be used to block the opioid receptors to avoid any clinical effects or side-effects of fentanyl.

Blood samples will be obtained as follows (based on administration route):

- 60 min pre-IV administration and then up to 36 hr (1.5 days) post start of IV administration
- 60 min pre-application and then up to 192 hr (8 days), during 3 day wear and post removal of RLD
- 60 min pre-application and then up to 192 hr (8 days), during 3 day wear and post removal of Generic product

B) Residual Drug Analysis determination of Strength

In conjunction with the above described study residual drug analysis will also be conducted for the used RLD and Generic TDDS described in Part A.

- Prior to administration to the Subject as described in Part A, the TDDS will be weighed and the weight recorded.
- The pouch, release liner and all items coming into contact with the TDDS (gloves, forceps, etc.) to be applied in Part A will be retained for analysis.
- The used TDDS will be retained for drug content analysis.
- Upon removal of the product after prescribed wear Session, the skin (at site of application) will be swabbed and the swab retained for drug content analysis.
- All items coming into contact with the TDDS during removal from the Subject and storage in a separate labeled sealable foil pouch for analytical retention will be analyzed for drug content.

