3 OBJECTIVES

3.1 Study Objectives

The objectives of this open label, randomized, crossover study are to

- To explore bioequivalence of Duragesic® transdermal system and generic Mylan fentanyl TDDS, and compare bioavailability to direct IV infusion of fentanyl citrate.
- To conduct release rate analysis of generic fentanyl (Mylan) TDDS compared to Duragesic® TDDS.
- To determine the residual drug content of the Duragesic® and generic fentanyl TDDS.

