4 STUDY DESIGN

This is a three treatment open-label, randomized cross-over clinical study with a Run-In Study Session I of intravenous fentanyl citrate, followed by randomization to Duragesic® and generic fentanyl in a sequential, 2-Session fashion with at least a one week wash-out Session between the sessions.

The study design is shown below:

Study Session I (Run-in)	Randomization		Study Session II	Study Session III
Intravenous -Fentanyl		Study Arm 1	Duragesic®	Mylan Fentanyl
		Study Arm 2	Mylan Fentanyl	Duragesic®

The study will consist of a total of twenty-five Study Days (24 Subjects) within three Study Sessions, with at least a one week washout Session between successive Study Sessions. The half-life of fentanyl is approximately 24 hours. Hence, 5 days (i.e. 5 half-lives) will be sufficient for >95% of fentanyl to be eliminated from the body. Each of the 24 Subjects will be enrolled to complete all twenty-five study days (Run-In Study Session I = 5 Study Days; Study Sessions II and III = 10 Study Days each). The study is open label and not blinded, because PK assessment is not subject to participant and/or observer bias. After each Study Session is completed, the available safety data will be reviewed by an Independent Safety Monitor (ISM) to determine whether or not to proceed to the next Study Session.

Considering the objective of the study to explore bioequivalence of Duragesic® and generic fentanyl and to conduct release rate analysis of generic fentanyl to Duragesic®, the above study design would adequately address both questions. The randomization to sequences [Reference (R) –Test (T), T-R] would appropriately take into account the sequence and the Session effect for bioequivalence evaluations. Having all Subjects enter the intravenous Run-In Study Session I initially would also help in accurate determination of absolute bioavailability for Duragesic® and generic Mylan fentanyl in this study.

Each Subject will be his/her own control and each Subject will sign an institutional review board-approved consent form explaining the purpose, nature, risks, benefits, and duration of the study. The study will be conducted in accordance with good clinical practice guidelines and with the ethical principles originating in the Declaration of Helsinki.

The three Study Sessions are as follows:

Study Session I (Run-in):

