Each of the 24 Subjects will start the study with the Run-In Session of intravenous fentanyl citrate infusion by giving a single-dose of 100 µg fentanyl citrate infusion (2 mL over 2 minutes) as described in the Manual of Procedures. Each Subject will receive a naltrexone hydrochloride 50 mg oral tablet 12-17 hours ± 1 hour before and again shortly prior to intravenous administration and then as described below after intravenous administration for 7 additional doses, for a total of nine 50 mg oral doses of naltrexone hydrochloride tablets.

Study Session II:

Twelve Subjects will be randomized to Study Arm 1 which will receive the Duragesic® fentanyl TDDS (25 µg/h); and other 12 Subjects to Study Arm 2 which will receive the Mylan fentanyl TDDS (25 µg/h). The patches will be applied for 3 days on each Subject. The Subject's skin in the area of application (upper arm region) will be relatively free of hair before TDDS application. Each Subject will receive a naltrexone hydrochloride 50 mg oral tablet 12-17 hours ± 1 hour before and again shortly prior to patch application and then as described below after patch application for 16 additional doses, for a total of eighteen 50 mg oral doses of naltrexone hydrochloride tablets.

Study Session III:

The 12 Subjects who were randomized to Study Arm 1 to receive the Duragesic® fentanyl TDDS (25 µg/h) will cross-over to receive the Mylan fentanyl TDDS (25 µg/h) applied; and the other 12 Subjects who were randomized to Study Arm 2 to receive the Mylan fentanyl TDDS (25 µg/h) will now cross-over to receive the Duragesic® fentanyl TDDS (25 µg/h). The patches will be applied for 3 days on each Subject. Each Subject will receive a naltrexone hydrochloride 50 mg oral tablet 12-17 hours ± 1 hour before and again shortly prior to patch application and then as described below after patch application for 16 additional doses, for a total of eighteen 50 mg oral doses of naltrexone tablets.

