5 STUDY ENROLLMENT AND WITHDRAWAL

Only adult Subjects who meet the inclusion/exclusion criteria will be eligible for enrollment into this study. Twenty-four Subjects will be recruited and at least 10 alternates will be screened, as needed, to ensure that any dropouts will be replaced until a total of 24 Subjects complete all study procedures. The study population selected for this study includes healthy non-smoking adult men and women ages 18 to 45, inclusive. The selection criteria are designed to exclude persons who might have medical conditions that could pose a safety risk and persons whose medical conditions might interfere with the objectives and results of the study.

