8.2 Pharmacokinetics (PK) Analyses

8.2.1 Pharmacokinetic endpoints

- Area under the time curve from dosing time to last measurement time (AUC_{0-t}) and peak drug activity (C_{max}) for Duragesic® TDDS and Mylan fentanyl TDDS will be used as the primary endpoint. For intravenous fentanyl, $AUC_{0-\infty}$ will be determined.
- The time to maximum concentrations (T_{max}) and $AUC_{0-\infty}$ for fentanyl from Duragesic® TDDS and Mylan fentanyl TDDS will also be determined.

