8.3 Final Analysis Plan

The primary statistical analysis will be performed on the natural log transformed AUC_{0-t} , AUC_{0-A} and C_{max} of Fentanyl from the three Study Sessions using SAS V 9.3. A linear mixed effects model will be used to assess the effects of treatment, Session, sequence and Subject within sequence on natural log transformed AUC_{0-t} , AUC_{0-C} and C_{max} . The treatment, Session, sequence effect will be treated as fixed effects and assessed at a significance level of 0.05. The Subject within sequence will be treated as a random effect. Intra and inter individual variabilities will be obtained. The least square mean estimates for the adjusted differences between treatment means (the log transformed AUC_{0-t} , AUC_{0-C} and C_{max}) and the standard error associated with these differences will be obtained. The geometric means for AUC_{0-a} will be obtained by exponentiating the log transformed AUC_{0-i} for all the three treatments to determine the absolute bioavailability.

The absolute bioavailability for Duragesic® TDDS and Mylan fentanyl TDDS will be calculated.

The analyses for IV administration of fentanyl citrate will be as follows:

Non compartmental and compartmental analyses will be conducted to estimate the PK parameters such as clearance, volume of distribution, elimination rate constant, maximum serum concentration; time of maximum serum concentration and area under the serum concentration-time curve. All analyses will be conducted using Phoenix® WinNonlin® 6.3 (Pharsight, a Certara Company, CA). Absolute bioavailability will be calculated.

The analyses for both TDDS applications (Duragesic® and Mylan fentanyl) will be as follows:

The serum fentanyl concentrations will be determined and the PK parameters such as C_{max} , T_{max} , AUC, steady concentrations (C_{ss}) of fentanyl in each Subject will be elucidated. The rate of fentanyl absorption in each Subject is calculated by dividing the C_{ss} by the clearance predicted from the IV bolus data.

Cumulative amount of fentanyl released by Duragesic® at the end of study Session will be obtained by subtracting residual fentanyl still remaining in the TDDS at the end of the study Session from the total amount of the drug present in an unused TDDS.

Similarly, cumulative amount of the drug released by the Mylan TDDS at the end of study Session is computed.

The rate of drug release from Duragesic® and Mylan TDDS will be determined.

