The means of fentanyl release rates from Duragesic® TDDS, standard deviations from their mean, and 95% confidence intervals will be determined and tabulated. The statistical significance of difference between the means will be evaluated by two-tailed Student's t-test.

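### Release rate is compared by an unqualified Student's t-test outside the planned crossover model, with no confidence interval for the Mylan–Duragesic difference (minor)

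*Combined protocol and SAP*

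**What the plan says.** All references are to the combined protocol and SAP.

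- **Objective (section 3.1).** The second of three objectives is "To conduct release rate analysis of generic fentanyl (Mylan) TDDS compared to Duragesic® TDDS".
- **Design (Protocol Summary and section 4).** "Each Subject will be his/her own control". After the IV run-in, subjects wear one patch in Session II and the other in Session III. "Twelve Subjects will be randomized to Study Arm 1", and the other twelve go to the reverse order. Section 4 says that randomising to sequences "would appropriately take into account the sequence and the Session effect for bioequivalence evaluations".
- **Completers (section 5).** "any dropouts will be replaced until a total of 24 Subjects complete all study procedures".
- **Primary endpoints (section 8.2.1).** AUC to the last measurement and Cmax for the two patches "will be used as the primary endpoint". Release rate is not among them.
- **Crossover model (section 8.3).** "A linear mixed effects model will be used to assess the effects of treatment, Session, sequence and Subject within sequence on natural log transformed" AUC and Cmax, using data from all three Sessions. Release rate is not named.
- **Release rate (end of section 8.3).** The rate is to be determined for both products. The sentence on tabulating means, standard deviations and 95% confidence intervals names only Duragesic. The comparison is then a single sentence: "The statistical significance of difference between the means will be evaluated by two-tailed Student's t-test".

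**The concern.** The trial pays for a crossover and specifies a crossover model, but does not apply it to release rate. Three things follow.

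1. **No interval for the comparison.** The objective is comparative, and the only planned comparative output is a p-value. A non-significant result in 24 subjects would not show that the products release drug at similar rates. Separate intervals for two correlated means do not give the interval for their difference.
2. **Session is ignored.** Neither form of Student's t-test removes a shift between Sessions II and III. In a paired test, the shift enters the differences with opposite signs in the two sequences and inflates their variance.
3. **The form of the test is unstated.** Two analysts could run a paired and an unpaired test on the same data, and both would be following the plan.

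**Working it through.** **Inputs.** From the documents: 24 completers, 12 per sequence, each measured on both patches; two-tailed test. The 0.05 level is stated for the mixed model and is assumed here for the t-test. The documents give no SD, within-subject correlation, Session effect, margin or power for release rate, so there is no planned figure to reproduce. The following are assumptions: SD of one product's release rate = 1; correlation ρ between a subject's two values from 0 to 0.7; Session effect π of 0, 0.25 or 0.5 SD.

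**Half-width of the 95% CI for the difference (n = 24, in SD units)**

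- Unpaired: t(46 df) × √(2/n) = 2.013 × 0.2887 = 0.581 at every ρ.
- Paired, no Session effect: t(23 df) × √(2(1−ρ)/n). At ρ = 0.5: 2.069 × 0.2041 = 0.422.
- Crossover model: t(22 df) × √(2(1−ρ)/n). At ρ = 0.5: 2.074 × 0.2041 = 0.423, whatever the Session effect.
- Paired, with Session effect π: the differences are shifted by +π in one sequence and −π in the other, so their variance becomes 2(1−ρ) + π² × 24/23. At ρ = 0.5, π = 0.5: 2.069 × √(1.261/24) = 0.474.

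| ρ | Unpaired | Crossover | Paired, π = 0.5 |
|---|---|---|---|
| 0 | 0.581 | 0.599 | 0.635 |
| 0.1 | 0.581 | 0.568 | 0.606 |
| 0.3 | 0.581 | 0.501 | 0.544 |
| 0.5 | 0.581 | 0.423 | 0.474 |
| 0.7 | 0.581 | 0.328 | 0.392 |

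The mean half-widths in simulation are about 1% smaller, because a sample SD slightly underestimates the true SD on average. The cost of the Session term is one degree of freedom: 2.0739 / 2.0687 = 1.0025, an interval 0.25% wider.

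**Power and size.** These come from 400,000 simulated 12/12 crossovers per setting. The true difference is set for 80% paired power without a Session effect: 0.845, 0.801, 0.707, 0.597 and 0.463 SD for ρ = 0, 0.1, 0.3, 0.5 and 0.7. A separate run of 200,000 per setting gave the same results within simulation error. Cells show power / size in %.

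| ρ | Paired, π = 0 | Paired, π = 0.25 | Paired, π = 0.5 | Unpaired, π = 0 |
|---|---|---|---|---|
| 0 | 80 / 5 | 79 / 4.6 | 76 / 3.8 | 82 / 4.9 |
| 0.1 | 80 / 5 | 79 / 4.6 | 76 / 3.7 | 79 / 4.0 |
| 0.3 | 80 / 5 | 79 / 4.5 | 75 / 3.4 | 70 / 2.0 |
| 0.5 | 80 / 5 | 78 / 4.3 | 72 / 2.9 | 54 / 0.7 |
| 0.7 | 80 / 5 | 77 / 3.9 | 67 / 2.0 | 26 / 0.1 |

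The crossover model has about 80% power and 5% size in every setting.

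**Reading the tables.** With 12 subjects per sequence the difference in means is unbiased under every analysis, and no analysis exceeds 5% size. Without a Session effect, the paired test and the crossover model are practically the same. The unpaired test loses nothing at ρ = 0, about 1 point at ρ = 0.1, and much more as ρ rises.

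**The case against.** The strongest reply is that the test is probably meant to be paired. The plan says twice that subjects are their own controls, and replacing dropouts protects the balance that makes a paired test valid. On that reading, and without a Session effect, changing the model gains nothing (half-width 0.422 against 0.423 SD at ρ = 0.5). No passage predicts a Session effect for release rate. Section 4 claims the Session adjustment only for bioequivalence, and the patch Sessions follow the same procedure with at least a week between them. The 67% power figure needs a Session shift of 0.5 SD, larger than the 0.463 SD treatment effect in that scenario. Release rate is not a primary endpoint, and no decision rule rests on it. Naming only Duragesic in the tabulation sentence looks like a slip.

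Most of this stands. It shows that the plan is under-specified, not that an unpaired test is intended, and it keeps the point minor. It does not supply the missing interval. The confidence intervals are mentioned together with the Duragesic means and standard deviations, and reading them as an interval for the difference strains the sentence. That nothing prevents an analyst from reporting such an interval is no substitute for planning it when the comparison is a stated objective. Nor does the expectation of a small Session effect argue against adjusting for one, since the adjustment is almost free.

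**Conclusion.** The concern holds and is minor. The firm part needs no assumed numbers: a comparative objective gets an unqualified t-test, no interval for the difference is planned, and the trial's own crossover model is not used.

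The size of the loss rests on an assumed correlation and Session effect. On the likelier paired reading it runs from nothing (no Session effect), through 1 to 3 points of power (0.25 SD), to 4 to 13 points (0.5 SD). On the less likely unpaired reading without a Session effect, power is 70%, 54% and 26% at ρ = 0.3, 0.5 and 0.7, against about 80% for the crossover model. Every form errs on the conservative side, so the risk is a missed or imprecisely described difference, not a false positive.

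**What to change.** In section 8.3, replace the t-test sentence with the following plan.

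- Analyse release rates from Sessions II and III only, since the IV Session has no patch release rate. Fit treatment, Session and sequence as fixed effects and Subject within sequence as random.
- Report the Mylan–Duragesic difference, or the ratio if the analysis is on the log scale, with its 95% CI.
- Tabulate means, standard deviations and 95% CIs for both products.
- If a t-test is kept, state that it is paired by subject and give the 95% CI of the paired difference.

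The cost is a few lines of SAP text and a two-Session, two-treatment version of the model, because the model as written takes in all three Sessions. It uses the same data and spends one degree of freedom. Nothing changes in the conduct of the trial.
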